4.1 Test Schedule

Tests reflect common Activities of Daily Living, important safety measures, ancillary data, and subject satisfaction and interaction with the APEX Device crucial for successful development of the APEX Device.

Table 3: Test Schedule

Outcome Measure	Notes	Visit		
		After consent and HIPAA authorization obtained	1	2
Medical History	CKRI research staff will gather pertinent medical history of subjects ahead of clinical visit.	X		
Mannequin Test #1: Object Movement	Can the subject manipulate the device on a mannequin to manipulate an object in space? (Assistive Grip Device Allowed for use)? (Yes/No)		Assisted	
Mannequin Test #2: Object Movement	Can the subject manipulate the device on a mannequin to manipulate an object in a preferred pathway (Assistive Grip Device Allowed for use)? (Yes/No)		Assisted	

with Intention				
Mannequin Test #3: Button Push	Can the subject manipulate the device on a mannequin to push an elevator button? (Yes/No)		Assisted	
Mannequin Test #4: Lift Cell Phone	Can the subject manipulate the device on a mannequin to lift a cell phone? (Yes/No)		Assisted	
Safety: Observational Data on uncontrolled device guided movement	Observe if uncontrolled device movement occurs (Yes/No)		X	
Time using Device	Record time subject spends using device		X	
Open Ended Feedback	Data recorded from study participants from set questions. (See Appendix 2)		X	
Data Review				X
Clinician Feedback				X

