Target user population will be three to six individuals with spinal cord injury at levels C3 to C5, and AIS A, B, or C. Inclusion and exclusion criteria are below:

3.1 Inclusion Criteria:

1. Spinal cord injury at levels C3 to C5, and AIS A, B, or C
2. Greater than 3-months post injury or surgery to spinal column, arms, or shoulder
3. Ability to provide informed consent
4. Age 18 or over
5. Selected for participation based on investigator discretion

3.2 Exclusion Criteria:

1. Unable to follow instructions
2. Exhibit significant behavioral problems or impaired cognitive ability
3. Inability to provide consent
4. Non-English speaker

Clinicians involved in overseeing the device manipulation portion of the study will be expected to provide feedback about the APEX device.

4. Study Design

Part 1: The study design will be that of a single-arm pilot study with three to six human subjects (n=3-6). The study will inform the AMI design team of customer and APEX design requirements needed to develop an APEX device for commercial release. Participants will be expected to attend one 180 minute session. AbiliTech Medical personnel will be present for user training, during all device evaluation sessions and to troubleshoot technical problems. Courage Kenny Rehabilitation Institute (CKRI) personnel will collect subject medical history from medical records once consent and HIPAA authorization are obtained. Appendix 1, section 1 includes subject information to be collected. Potential participants will receive the consent form ahead of time to read and study. At the start of visit 1, subjects will be consented as a group and sign the HIPPA authorization. During device testing, Appendix 2 and 3 include assessment forms for device testing and questions subjects will be asked. Appendix 4, includes the device feedback survey which will be completed onsite before conclusion of the study. Subjects will use their personal internet connected mobile device to access and complete the survey. If subjects do not have a mobile device, a tablet will be available for subject to use and complete the survey. Audio recordings will be taken and videos of the mannequin will be recorded during device movement. Table 1 highlights activities to be performed in the User Focus Group.

Table 1: Visit 1: User Focus Group Activities

	Activity	Description

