5.3 Post-Study Evaluations

None of the subjects will be followed or have data recorded after the visit, unless an adverse event is reported that relates to their participation in this study.

6. Outcomes

The fundamental purpose of conducting this pilot study is to examine the feasibility and safety of an APEX device, and examine the feasibility of an approach to ultimately be used in a larger scale study. Upon successful completion of the APEX Pilot Study, AbiliTech plans to submit for a Phase II NIH grant to complete product and clinical development on the path to commercial release of the APEX device.

The APEX Pilot Study includes assessments and other metrics that measure function and gather feedback as listed in Table 3.

Concept model device feasibility will be subjectively evaluated and defined as follows:

1. Manipulation of Mannequin: Were the users able to control the device with intention?
2. Usability Outcomes: User feedback on device performance, user input controls and overall comfort.
3. Clinician Feedback: Are there features that should be integrated into the device to enhance clinical utility?

Principal Investigator and Clinician feedback on overall device performance will be factored into the concept model feasibility results.

7. Criteria for Study Discontinuation

AbiliTech Medical will document any study participant subject discontinued from the APEX pilot study. The documentation will contain the rationale for study participant subject to be discontinued from the study. The PI must be notified immediately if a study participant subject discontinues the pilot study. Any data from the discontinued study participant subject will be maintained and may be used in the data analysis.

A study participant subject in this study may be discontinued for any of the following reasons:

- At the Investigator's discretion;
- At the subject's discretion;
- If the subject has a severe injury or illness within or outside of the study that affects their participation in the study;

8. Statistical Considerations

Data will be recorded and reported. No statistical analysis will be performed since the subject population is n=3-6. This study is designed to assess early feasibility and prepare for a larger clinical study in the future.

9. Retention of Records

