Appendix 2: Pilot Usability Testing Form

[name]
[contact] www.abilitechmedical.com

AbiliTech Medical APEX Study Pilot Usability Testing Form

Subject Information

Subject ID Number _____

Subject Assessment with APEX

Is the subject familiar with smartphone applications? Yes No

Can the subject use voice control features of the application to toggle between device modes? Yes No

Can the subject use the head worn accelerometer to control the APEX device movement? Yes No

Can subject power the device on/off? Yes No

Can the subject move the APEX on a mannequin in the following Ranges of Motion?

Shoulder

Flexion Powered ROM: 0 to 60° Yes No

Shoulder Abduction Powered ROM: 0 to 30° Yes No

Horizontal Internal Rotation Powered ROM: 35 to -35° Yes No

Compound Shoulder ROM (Flexion, internal rotation, horizontal adduction: limited in horizontal plane): 0 to 100° Yes No

Elbow

Elbow Flexion/Extension Powered ROM: 0 to 130° Yes No

Forearm

Supination Powered ROM: 0 to 60° Yes No

Pronation Powered ROM: 0 to 50° Yes No

Can the subject move the APEX on a mannequin to complete the following tasks?

Control APEX device to manipulate objects in space Yes No

Control APEX to move an object in a preferred pathway Yes No

Control APEX device to push buttons Yes No

Control APEX to lift a water bottle from table level Yes No

Control APEX to lift a phone Yes No

Uncontrolled device movement observed: Yes No (if yes, please comment below)

Time spent using the device: _____ (min)

Notes

Utility

1. On a scale of 1 to 5, how would the APEX System improve your ability to use your arms? (1 no improvement - 5 strong improvement)
2. In general, what would you like to be able to do with your arms?
3. What are three to five Activities of daily living that you wish you could perform, listed in priority?
4. Do you think using the APEX device you could do [each of the ADL they stated]?

Device Feedback

1. What is your general impression of the APEX System, knowing the development phase it is in?
2. Would you use the APEX System? How much? Where? When? For what Uses?
3. What do you like about the APEX System?
4. What do you dislike about the APEX device?

5. What could be improved about the APEX device?
6. What is your opinion about the size, appearance, texture, color, and/or noise of the APEX device?
7. What is your opinion on the control system?
8. What type of control system would you prefer?

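### The four primary mannequin tasks are each recorded as one Yes/No without an attempt count, so a Yes cannot separate reliable control from an occasional success

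*Combined protocol and SAP*

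**What the plan says.** Primary outcomes 1 to 4 (section 2) concern the user's ability to control the device in four tasks. Section 4.1, Table 3 turns each into one question with a Yes/No answer:

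- Test #1: "Can the subject manipulate the device on a mannequin to manipulate an object in space"
- Test #2: "Can the subject manipulate the device on a mannequin to manipulate an object in a preferred pathway"
- Test #3: "Can the subject manipulate the device on a mannequin to push an elevator button? (Yes/No"
- Test #4: "Can the subject manipulate the device on a mannequin to lift a cell phone? (Yes/No"

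Appendix 2, the form filled in during testing, repeats each task as one tick-box line, for example "Control APEX to move an object in a preferred pathway Yes No". The same form has one Yes/No box for uncontrolled device movement (with a comment if Yes), one field for total minutes of use, and a notes space. Section 4 adds that "videos of the mannequin will be recorded during device movement". Section 6 makes intentional control of the mannequin the first feasibility item and says that feasibility is judged subjectively. Section 8 states: "No statistical analysis will be performed since the subject population is n=3-6".

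**The concern.** The primary outcomes and the first feasibility item ask about control, and the label of Test #2 adds intention. A single tick records only that the task was judged achieved. It does not show how many tries were needed, whether the user had said beforehand where the object should go, or whether an unintended device movement contributed.

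Because no inference is planned, these ticks are the main task-level record of user control. They are part of the user results shown to the clinicians at Visit 2, and the study is meant to prepare for a larger one. A subject who succeeded once in ten tries and one who succeeded ten times in ten can look identical in that record, although they would lead to different design decisions.

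**Working it through.** **What is recorded for each task.** Table 3 and Appendix 2, read together with sections 4, 6 and 8, give:

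| Item | Test #1 | Test #2 | Test #3 | Test #4 |
|---|---|---|---|---|
| Object named | No | No | Elevator button | Cell phone |
| Target or path stated before the attempt | Not required | Not required | Object only; not which button | Object only; no height or hold |
| Attempts counted | No | No | No | No |
| Successes counted | No | No | No | No |
| Uncontrolled movement tied to the task | No | No | No | No |

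**Whether another part of the plan fills the gap.**

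- Uncontrolled movement is one box per subject. No rule says that it cancels a task Yes.
- Time is total minutes of use, not time per task.
- The mannequin video (section 4) and the motion capture data for the clinician group (section 4, Part 2) are not linked to task scoring.
- Table 1 places instruction, acclimation and operational testing in one 60-minute block. Nothing marks where practice ends and scored attempts begin.

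So no other section supplies an attempt count or a target declared in advance.

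**Illustration.** The plan has no figure to reproduce: it states no alpha, power or success threshold. Let p be the chance that one attempt succeeds without control, and k the number of attempts. Both are assumptions, and attempts are taken as independent. The chance of at least one success is 1 − (1 − p)^k:

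| p | k = 3 | k = 5 | k = 10 |
|---|---|---|---|
| 0.10 | 0.27 | 0.41 | 0.65 |
| 0.20 | 0.49 | 0.67 | 0.89 |
| 0.30 | 0.66 | 0.83 | 0.97 |

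For example, 1 − 0.8^5 = 1 − 0.328 = 0.672.

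**What a tally would add.** Take 5 attempts and look at the chance of 4 or more successes, 5p^4(1 − p) + p^5:

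- p = 0.10: 0.0005
- p = 0.20: 0.0067
- p = 0.30: 0.031
- with real control, p = 0.8: 0.74
- with real control, p = 0.9: 0.92

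At p = 0.2 against p = 0.8, the any-success tick gives 0.67 against 1 − 0.2^5 = 0.9997, while 4 or more of 5 gives 0.007 against 0.74. The count carries information that the tick discards. The 4-of-5 cut is used here only to show this and is not proposed as a pass mark.

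**The case against.** The strongest reply is proportion. This is a focus-group pilot with 3 to 6 subjects working a device on a mannequin, mainly to inform design. No threshold, test or sample size rests on the ticks, and investigator and clinician opinion also enters the feasibility judgement. That stands, and it keeps the point small. It does not remove it, because with so few subjects the detail recorded for each one is most of what the study yields.

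The form also holds other evidence of control. It asks whether the subject can steer the device with the head-worn accelerometer, and it scores seven movements against preset angular ranges. This stands in part: those items are also single Yes/No ticks, and they are not the primary outcomes.

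Three stronger readings are tempting, and the documents do not support them:

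- **A reader might infer that none of the four tasks has a target.** Tests #3 and #4 name an object. What is missing there is the attempt count and what counts as success.
- **A reader might infer that an unintended movement is scored as control.** The items ask about control, and a sensible assessor could refuse the tick. The plan merely lacks a rule requiring that, so such a movement can score Yes; it does not follow that it will.
- **A reader might infer that the error runs only in the favourable direction.** There is no minimum number of attempts either, so a subject stopped after one failure or during a technical fault could be marked No despite being able.

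The probabilities are also open to challenge. One p for four unlike tasks is artificial, learning breaks independence, and ten attempts per task may not fit the 60-minute block. They are illustrative only.

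**Conclusion.** The point holds as a cheap improvement. Each primary task is one Yes/No without an attempt count. The path in Test #2 and the end point in Test #1 need not be declared first, and uncontrolled movement is not recorded by task. A Yes can therefore mean anything from one success in many tries to reliable control, which limits what the primary outcomes say about intentional control.

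These features follow directly from the documents. The size does not: it depends on assumed values of p and k and on independent attempts, and the documents give none of these. Nor do they support expressing the effect as a shift in a success percentage, because the plan does not say that one will be calculated. No test, threshold or sample size is affected.

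**What to change.** On Appendix 2, for each of the four tasks:

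1. After acclimation, have the target or path stated before each scored attempt and write it down. For Tests #3 and #4, also note what will count as a press or a lift.
2. Record the attempts made and the attempts that reached the stated target.
3. Flag uncontrolled movement by task, and do not count as a success any attempt in which it moved the object.

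Report successes over attempts for each subject and task beside the planned Yes/No. The mannequin video can be used to check the counts. It cannot show intention by itself, since it films the device and not the participant, so the target has to be stated at the time. Recording the first-attempt result is optional, because in a single session it partly reflects learning. No minimum number of attempts is needed.

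The cost is a few extra form fields and a little time per attempt, with no added visit, staff or subjects. The reported results may look less favourable than a list of Yes ticks.

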1.4. Study Rationale

Currently there are no effective mobile devices that enable people with limited upper extremity movement to move their upper extremities, especially for individuals with upper level SCI (C1-5). This

severely limits independence, reduces the ability for individuals with this condition to complete ADL's and makes them dependent on caregivers to complete all physical interactions with their environment. We hypothesize that the APEX device can safely enable and control shoulder-elbow movement to improve ADL performance and independence. Individuals with upper level cervical spinal cord injury that have lost functional use of their arms have a high potential to increase their quality of life by using this device which justifies observing their interaction with the APEX Focus Group.

2. Objectives

Objectives:

Perform focus groups with subjects and clinicians to evaluate a proof of concept active powered prosthesis.

1. Perform a focus group with three to six individuals with chronic tetraplegia to evaluate the user control interface of an active powered prosthesis device proof-of-concept prototype. Subjects will provide feedback on the device function and usability after manipulating the device on a mannequin.
2. Perform a focus group with Courage Kenny Research Institute Clinicians to validate device safety features, performance and assess the potential clinical utility of the device.

Primary Outcomes:

The following will be assessed:

1. User ability to control APEX device to manipulate objects in space
2. User ability to control APEX to move an object in a preferred pathway
3. User ability to control APEX device to push buttons
4. User ability to control APEX to lift a phone
5. Evaluate subject reported outcomes within their interaction with the APEX device through interviews and a survey

Secondary Outcomes:

1. To observe and assess any uncontrolled device guided movement during the APEX device testing on mannequin
2. Gain clinician feedback on device safety control mechanisms

Ancillary Data:

1. Subject Acclimatization/ Learning Time to Operate the APEX Device.
2. Characterization of focus group population
 - a. Medical History: Diagnosis, level of injury, AIS classification
 - b. Subject examination: MMT scores
3. Feedback on device design
4. Feedback on user input control system

3. Trial Population

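### Do the extra water-bottle task on the Appendix 2 form and the missing grip-aid note for the phone lift call for a change to the plan?

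*Combined protocol and SAP*

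**What the plan says.** Section 2 and the synopsis give the same four task outcomes: moving objects in space, moving an object along a chosen path, pushing buttons, and "User ability to control APEX to lift a phone". A fifth primary outcome covers interviews and a survey.

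Table 3 in section 4.1 has one row for each of the four tasks. Test #1 is worded "Can the subject manipulate the device on a mannequin to manipulate an object in space? (Assistive Grip Device Allowed for use)? (Yes/No" and Test #2 asks whether the subject can "manipulate an object in a preferred pathway (Assistive Grip Device Allowed for use)? (Yes/No". The phone row, Test #4, is "Can the subject manipulate the device on a mannequin to lift a cell phone? (Yes/No", with nothing about a grip aid either way. All four rows are marked as assisted at Visit 1, and that word is not defined. Section 6 describes the study as including "assessments and other metrics that measure function and gather feedback as listed in Table 3".

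The Appendix 2 form repeats the four tasks, among them "Control APEX to lift a phone Yes No", and adds "Control APEX to lift a water bottle from table level Yes No". None of the five lines mentions a grip aid, and the form has no box for one. It does have a Notes space. Section 4 names Appendix 2 as an assessment form for device testing. Section 8 states that data are recorded and reported, with no statistical analysis because of the sample size of 3 to 6.

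**The concern.** Two things look wrong when the form is laid against the table.

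First, the bottle lift is the same kind of task as the phone lift. It sits in the same block of the form as the four primary tasks, and nothing marks it as different. With no stated status, lifting performance might be described with or without it once the results are known.

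Second, a lift needs the object to be held, and the powered movements listed on the form are shoulder, elbow and forearm only. If holding depends on an aid, the answer to the phone item could depend on the set-up as well as on the user's control of the device. Table 3 treats the aid as relevant to two tasks and is silent on the lift that is a primary outcome. If one subject had an aid and another did not, their answers would not mean the same thing. Each subject attends a single session, so a retest is unlikely.

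**Working it through.** The plan has no sample-size or power figure on this point, so the check is a comparison and a count.

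**1. Tasks**

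| Task | Section 2 outcome | Table 3 row | Grip aid in Table 3 | Appendix 2 line |
|---|---|---|---|---|
| Object in space | yes | yes | allowed | yes |
| Chosen path | yes | yes | allowed | yes |
| Button push | yes | yes | not stated, nothing held | yes |
| Phone lift | yes | yes | not stated | yes |
| Water-bottle lift | no | no | no row | yes |

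The form has 5 tasks and Table 3 has 4, so 5 − 4 = 1 extra. Within Table 3, three tests involve an object to be held and two of them carry the grip note. The bottle's missing note follows from its missing row and is not a second gap.

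**2. Entries touched.** Two lift items × 3 to 6 subjects = 6 to 12 Yes/No entries. The phone item alone gives 1 × 3 to 6 = 3 to 6 entries, and only these belong to a primary outcome.

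**3. Is absence from Table 3 unusual?** Count the Yes/No items on the form:
- 4 opening items (smartphone familiarity, voice control, accelerometer, power on/off)
- 7 ranges of motion (shoulder 4, elbow 1, forearm 2)
- 5 tasks
- 1 item on uncontrolled movement

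The total is 4 + 7 + 5 + 1 = 17. Table 3 has rows for 4 tasks and for uncontrolled movement, so 17 − 5 = 12 items have no row, and the bottle is 1 of those 12. The Appendix 4 survey, part of the fifth primary outcome, has no explicit row either. Table 3 is therefore a schedule of the main assessments and does not list every recorded item.

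**4. Can a bottle result alter a primary result?** The primary outcome names a phone. No outcome combines the lifts, and there is no success threshold and no test. A bottle result, whatever it is, leaves the phone count unchanged. Under section 8 it is reported because it was recorded.

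**5. Can a failed phone lift be interpreted?** The form has items that test control with nothing held: "Can the subject use the head worn accelerometer to control the APEX device movement? Yes No" (1), the ranges of motion (7) and the button push (1), so 1 + 7 + 1 = 9 per subject. A subject who passes these but fails the lift points towards holding or fine positioning. One who fails them too points towards control. Section 4 also provides for video of the mannequin during movement, which should show whether an aid was fitted, and for sponsor staff at every session. The form's Notes space takes the rest.

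**6. The assisted label.** It is entered for the button push as well, where nothing is held, so it is unlikely to refer to the grip aid. Leaving it undefined does not affect the grip question.

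**The case for a change.** The strongest case for a change is that, with no statistical analysis, the item definitions are all that give the counts meaning. A statement that some number of subjects lifted the phone is hard to read if the set-up was neither fixed nor recorded. Even for Tests #1 and #2 the aid is permitted and not required, so its use may differ between subjects with no box to show it. The results go to the clinicians at Visit 2 and support a later grant application. The correction would be cheap.

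Part of this stands. The set-up for the phone lift is unstated, the form has no dedicated box, and video and notes explain a result afterwards but do not fix a common set-up beforehand. A small ambiguity would also remain if the phone needed finer positioning than the button.

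The reporting argument does not stand, since recorded data are to be reported and the primary item is named explicitly. The comparability argument is limited. The object is held on the mannequin's side, so holding is mainly a property of the rig that the same staff set up for a few subjects. Section 6 judges feasibility subjectively, drawing on user control, user feedback and clinician feedback, and no single lift item decides it.

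**Conclusion.** The mismatch is real but does not call for a change to the plan. One of the five form tasks lacks a Table 3 row and an outcome level, which is a clerical slip. One primary task lacks a set-up note, which is a detail that staff would ordinarily settle by using the same arrangement for everyone and noting any departure. No stated rule or number is wrong, and no result or conclusion of the study would differ.

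This rests on three assumptions. Section 8 is taken at its word, so the bottle entries are reported beside the others, most naturally as supplementary to the four named tasks. The Notes space and mannequin video are used as section 4 and Appendix 2 provide. The study also stays descriptive with no success threshold. If the phone item were carried into a later study as a formal endpoint, its set-up would need to be defined there.
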